3.1.1 Storage and Handling of Study Drug

All study drug received, will be stored, and handled strictly in accordance with the product label and the site standard operating procedures (SOPs). Upon receipt, the study drug will be promptly transferred to the environmentally controlled Drug storage area. The research staff will examine the shipment and temperature monitoring devices (if applicable) to verify that the study drug was received in acceptable condition. Once inspected, the study drug will be stored in a restricted access, secured area with access limited to authorized research study staff, under physical conditions consistent with the study drug's specific requirements. After study drug is dispensed to subjects, the remaining study drug will be returned to storage in a restricted access, secured area under physical conditions consistent with the study drug's specific requirements. Study participants will be instructed to store the investigational product at room temperature at home, out of the reach of children.

3.2 Study Drug Accountability

The Investigator and designated study staff will maintain accurate records of receipt of all study drugs, including dates of receipt. The study staff will enter the lot number and expiration date on the Master IP accountability log. In addition, accurate records will be kept regarding when and how much study drug is dispensed and used by each patient in the study. Reasons for departure from the expected dispensing regimen will be recorded.

3.3 Method of Assigning Patients to Treatment Groups

After a patient signs the ICF at Screening (Visit 1), The investigator will randomly assign a study drug kit number for dispensing the study drug. The Kit number, expiration date will be noted on the individual IP dispensing log.

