The neurocircuitry implicated in altered threat and reward learning as mechanisms of risk for MDD includes the salience network (dorsal anterior cingulate cortex and anterior insula) and striatum. Notably, this neurocircuitry overlaps with dopaminergic and serotonergic pathways targeted by atypical antipsychotic medications^{15,16}. As such, altered neurocircuitry encoding of threat and reward learning could potentially be predictive of clinical outcomes for adjunctive therapies that target these pathways, such as lumateperone. There are two main routes by which these pathways could have clinically predictive significance. First, individual differences in neurocircuitry encoding of threat and reward learning could operate as markers of who would vs would not benefit from lumateperone adjunctive therapy. Second, pre- to post-treatment changes in neurocircuitry encoding of reward and threat learning could operate as a mechanism of symptom reduction (e.g., lumateperone induced improvements in reward and threat neurocircuitry encoding mediate reductions in depression symptoms). These possibilities are not mutually exclusive, and both would have considerable clinical significance for enabling precision medicine approaches to the treatment of MDD among early life trauma populations.

6. Design and Methodology

Provide a brief description of the overall study design or data collection methodologies. Details regarding protocol specific research procedures will be discussed in the next section below.

This is a single site investigator initiated randomized, double-blind, placebo controlled, fixed-dose study in patients with a primary diagnosis of MDD, a history of early life abuse, and who have an inadequate response to on-going SSRI treatment. The study will enroll a total of 50 participants (n=50) with 25 randomized to treatment and 25 to a placebo, and will be conducted in 3 phases:

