Screening Period - After signing the ICF, an identification number will be assigned to the subject. Prior to randomization, all subjects will enter a 2 week-day screening period (Screening) to determine eligibility. Eligible subjects must meet the Diagnostic and Statistical Manual of Mental Disorders, Fifth Edition (DSM-5) criteria for MDD without psychotic features, based on the DIAMOND (Diagnostic Interview for Anxiety, Mood, and Other Neuropsychiatric Disorders), with a current major depressive episode of at least 8 weeks in duration. They must have had an inadequate response (<50% symptom reduction) to an adequate trial of at least 1 antidepressant therapy (ADT) (as determined by administering the Massachusetts General Hospital Antidepressant Treatment History Questionnaire [ATRQ]) in their current Major Depressive Episode (MDE). During Screening Period (2 weeks) patient eligibility will be assessed and a Pre-dose fMRI performed.

Double-blind Treatment Period - Double-blind Treatment Period (6 weeks) during which all eligible patients will be randomized to receive lumateperone 42 mg or placebo in 1:1 ratio. At Baseline (Visit 2), patients who continue to meet all eligibility criteria will be randomized to either lumateperone or placebo.

Safety Follow-up Period in which all patients will return to the clinic for a safety follow-up visit approximately one week after the last dose of study treatment. All patients will complete a post dose MRI 1 week after the 6-week study period is completed.

- During the Pre-Dose and Post-dose MRI, Participants will undergo standard structural imaging as well as functional imaging during computational threat and reward learning tasks. Computational neuroimaging approaches will characterize neurocircuitry encoding of anticipating and delivery of threat and reward outcomes, enabling testing of predictors of lumateperone clinical response and mechanism of treatment action.

- Patients who discontinue study drug prior to Week 6 but agree to continue participation in the Double-blind Treatment Period (DBTP) should be seen at all subsequent protocol-defined visits up to week 6 and should also return for the SFU Visit for post dose MRI. Study drug will no longer be dispensed for these patients and the clinical management of these patients will be at the discretion of the Investigator.

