 - At Baseline (Visit 2), patients who continue to meet all eligibility criteria will be randomized to 1 of 2 treatment arms, lumateperone 42 mg or matching placebo, and will enter the 6-week DBTP. Patients will be administered the first dose of study drug in the evening of the Baseline Visit (Visit 2/Day 1). A single dose will be taken each evening, with or without food, for the duration of the 6-week DBTP.
 - MRI assessments will be completed at baseline Pre- dose and post dose at 1-week safety follow up visit.

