14. ECG abnormalities where the patient has corrected QT interval using the Fridericia formula (QTcF) $> 450 \text{ msec}$ for males or $> 470 \text{ msec}$ for females and/or heart rate $< 50 \text{ bpm}$, or evidence of clinically significant bundle-branch blocks at Screening (Visit 1);
15. The patient has any of the following conditions:
 - i. Cardiac: uncontrolled angina, or history of a myocardial infarction within 3 months prior to screening, or history of a clinically significant cardiac arrhythmia including antipsychotic drug-induced corrected QT interval prolongation, or any other cardiac disorder;
 - ii. Malignancy: Any diagnosis of cancer (except basal or squamous cell skin carcinoma), unless in remission for at least 5 years;
 - iii. Gastrointestinal: history of gastric bypass or any other condition that results in malabsorption;
 - iv. Endocrine: hypo- or hyperthyroidism unless treated and stable with no medication changes for at least three months prior to screening, diabetes, unless considered stable with no changes in treatment for at least three months prior to screening;
 - v. Hepatic: Hepatitis B or Hepatitis C; moderate or severe hepatic impairment (Child-Pugh B or C);
 - vi. Pulmonary: history of diagnosed and untreated obstructive sleep apnea;
 - vii. Neurological: history of epilepsy, seizure or convulsion, or electroencephalogram with clinically significant abnormalities, delirium, dementia, amnesia, or central sleep apnea, or significant brain trauma, or other cognitive disorder; History of movement disorders.
 - viii. Infectious: History of human immunodeficiency virus (HIV) infection.

Note: Any other medical condition, or medical conditions that are stable with treatment (eg, hypertension, hypercholesterolemia, or thyroid abnormalities) are allowed as long as the condition has been stable for at least 3 months prior to Screening (Visit 1); treatments for these conditions are documented, kept stable, and are expected to be unchanged during the study; and the condition is

not thought to affect safe participation in the study or relevant study outcomes in the opinion of the Investigator.

Other Criteria:

16. The patient is judged by the Investigator to be inappropriate for the study;
17. Patient is homeless;
18. Patient does not speak english;

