2.3 Rescreening

Individuals who sign the ICF to participate in the study but who do not subsequently meet all the requirements as outlined in the inclusion and exclusion criteria and therefore are not randomized (screen failures), may be rescreened once, at the discretion of the Principal investigator with the exception of subjects presenting with alcohol or drug abuse or previously undisclosed psychoactive drugs; subjects excluded because of QTc prolongation or other serious medical conditions at initial screening.

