4.2.2 Baseline (Visit 2 Week-1)

Subjects continuing to meet all eligibility and inclusion criteria and no exclusion criteria, will be randomized within each group at Baseline to start the study treatment.

1. Assessment scales: MADRS, CGI-S C-SSRS, HAMD-17, GAD-7, PHQ-9, QIDS-SR-16, and EQ 5D-5L.
2. Vital signs, including body temperature, systolic and diastolic BP, HR, pulse oximetry, and RR measures after the subject has been resting for at least 3 minutes.
3. ECGs taken pre-dose.
4. fMRI will be obtained.
5. EMA wellness App
6. AE if applicable
7. Laboratory tests, consisting of: blood sample for Hematology
8. POC: Urine drug test, pregnancy test (if applicable) and Breath Alcohol test

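### Section 3.3 has the investigator assign a kit at random after consent at Screening, whereas the rest of the protocol randomises still-eligible patients at Visit 2

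*Protocol*

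**What the plan says.** Protocol section 3.3, Method of Assigning Patients to Treatment Groups, describes the step in one sentence: "After a patient signs the ICF at Screening (Visit 1), The investigator will randomly assign a study drug kit number". A second sentence covers logging the kit number and expiry date.

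Other sections place the step later:
- Section 6, Design and Methodology: "Prior to randomization, all subjects will enter a 2 week-day screening period", and then "At Baseline (Visit 2), patients who continue to meet all eligibility criteria will be randomized to either lumateperone or placebo".
- Section 7, Study Procedure Description, under the double-blind period: "At Baseline (Visit 2), patients who continue to meet all eligibility criteria will be randomized to 1 of 2 treatment arms".
- Section 4.2.2, Baseline: subjects who continue to qualify "will be randomized within each group at Baseline to start the study treatment".
- Section 2.3, Rescreening: people who signed the consent form but did not meet the criteria "therefore are not randomized (screen failures), may be rescreened once".

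Section 6 sets a 1:1 ratio and a total of 50, "with 25 randomized to treatment and 25 to a placebo"; section 15 repeats the numbers. Exclusion criterion 16 in section 2.2 reads: "The patient is judged by the Investigator to be inappropriate for the study". Section 3.4 provides for identical packaging and similar appearance. Section 3.5 refers to a blinding code that can be broken in an emergency or by Drug Safety. The primary estimand in section 11.3 covers patients who were randomised and received a dose.

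**The concern.** Two procedures are written down for one act. Staff following section 3.3 would attach a kit, and with it a treatment, to every person who consents. Staff following section 4.2.2 would do so only for those who pass the Visit 2 checks, up to about two weeks later.

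The 3.3 version is the weaker of the two. Assignment should come after the decision to enrol, and whoever makes that decision should not be able to influence or foresee the assignment. Under 3.3 the kit is already chosen when the Visit 2 eligibility checks and the discretionary criterion 16 are applied, and the investigator is both the one who picks and the one who may exclude. A patient given a kit at Visit 1 and excluded before the first dose would fall outside the primary analysis population. Screen failures could use up assignments. A random pick by the investigator is also not, in itself, a 1:1 list, so the 25/25 split rests on something that section 3.3 does not state.

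**Working it through.** **1. Timing, side by side.**

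| Section | When the assignment is made | In whom |
|---|---|---|
| 3.3 | After consent, Screening (Visit 1) | Anyone who has signed |
| 6 | Baseline (Visit 2), after screening | Patients still meeting all criteria |
| 7 | Baseline (Visit 2) | Patients still meeting all criteria |
| 4.2.2 | Baseline | Subjects still meeting all criteria, by an undefined group |
| 2.3 | Implied: after screening | Not screen failures, although they signed |

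The kit determines the treatment, so assigning a kit is the randomisation. Sections 3.3 and 2.3 cannot both hold: under 3.3 a screen failure already has a kit, under 2.3 that person was never randomised.

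**2. The stated split.** 50 patients at 1:1 is 50/2 = 25 per arm, which reproduces the plan's figure. The question is whether the 3.3 step delivers it. The protocol does not state the kit supply or the screen-failure rate, so three assumptions are shown.

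(a) Each pick is an independent 50:50 draw, Binomial(50, 0.5):
- P(exactly 25/25) = C(50,25) × 0.5^50 = 11.2%
- P(30/20 or more uneven) = 20.3%

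(b) Kits are exactly balanced among S consented patients, 50 of whom go on regardless of arm, and kits of screen failures are not reused. The number on one arm is then hypergeometric, P(k) = C(S/2, k) × C(S/2, 50−k) / C(S, 50):

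| Assumed screen failure | S | Exactly 25/25 | 28/22 or more uneven |
|---|---|---|---|
| 30% | 72 | 20.2% | 20.0% |
| 40% | 84 | 17.6% | 26.6% |
| 50% | 100 | 15.8% | 31.7% |

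(c) Exactly 25 active and 25 placebo kits are supplied, and all end up with randomised patients: the split is 25/25 with certainty.

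So the result depends on a supply arrangement that the protocol does not give. The 3.3 step neither guarantees the split nor rules it out.

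**3. What imbalance costs.** With a common variance, the standard error of a difference in means is proportional to √(1/n₁ + 1/n₂).
- 25/25: 1/25 + 1/25 = 0.0800
- 28/22: 1/28 + 1/22 = 0.0812; ratio √(0.0812/0.0800) = 1.007, an increase of about 0.7%
- 30/20: 1/30 + 1/20 = 0.0833; ratio √(0.0833/0.0800) = 1.021, an increase of about 2%

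In power terms, for an assumed standardised effect of 0.8 (the protocol gives none), 25/25 has 80.7% and 21/29 has 79.7%.

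**4. Selection bias.** The documents contain nothing from which its size could be computed.

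**The case against.** The best defence is that section 3.3 only gives an order: consent first, then a kit for dispensing. Dispensing starts at Baseline (section 3.1 and Table 1), and sections 6, 7, 4.2.2 and 2.3 all point to Visit 2, so the intention is probably Visit 2. That is likely right about intention. It does not remove the conflict, because 3.3 names Visit 1 and no other visit and is the section that site staff would consult.

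A second defence concerns the harm. Packaging is identical, a treatment code exists, and an exclusion made before the first dose by someone blind to the kit's content is unrelated to arm. Early assignment alone therefore does not bias the comparison; the investigator would also have to learn or infer what the kit holds. This stands. A reader might infer that concealment is broken, that kit patterns can be guessed, or that the investigator who assigns the kit also scores the Visit 2 MADRS that decides eligibility. The documents support none of these. They describe no kit pattern, and section 7.4 gives the MADRS to the site's rater without saying that this is the assigning investigator.

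A third defence is that list generation, custody and block size commonly belong in a randomisation plan that is not shown. That also stands, and their absence is not the point here. The point is the step that the protocol does state.

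**Conclusion.** The contradiction is real and section 3.3 is wrong as written. It puts assignment before the eligibility decision, gives the pick to the investigator who holds discretionary exclusion, and names no mechanism that yields 25/25. What is missing is protection of the allocation; a failure of it has not been shown.

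The imbalance probabilities are arithmetically correct, but they rest on assumptions about kit supply, reuse of kits and screen failure that the protocol does not state. It is tempting to read them as serious damage to the trial, yet a 30/20 split costs only about 2% in standard error. The case for changing the text rests on the conflicting timing and the integrity of allocation, and not on power. A faulty allocation cannot be repaired once patients have been assigned.

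**What to change.** Rewrite section 3.3 along these lines: at Visit 2, after all inclusion and exclusion criteria have been confirmed and recorded, the patient receives the next kit in sequence; kits are numbered in advance from a computer-generated 1:1 list that the person judging eligibility neither prepares nor holds. This adopts the timing already in sections 6, 7 and 4.2.2, agrees with section 2.3, and means that screen failures use no assignment.

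In section 4.2.2, delete the reference to groups or say which groups are meant. Block size and any stratification can be left to the randomisation plan. If strata are used, some blocks may be incomplete at 50 patients, so the split should then be described as a target.

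The cost is one paragraph, one phrase and a list generated in advance, with no added visits or patients and no change in N.

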3.4 Blinding

The study will be performed in a double-blind manner. All study drugs will be supplied in identical treatment cards and packaging, and will be similar in color, smell, taste, and appearance, thereby enabling double-blind conditions.

3.5 Unblinding

Unblinding will be done only in an emergency that requires the study drug to be identified for the medical management of the patient. The Investigator will notify the Sponsor or designee immediately and a full written explanation must be provided if the blind is broken. Breaking the blinding code will immediately disqualify the patient from further participation in the study.

Treatment codes may be broken by Drug Safety for regulatory reporting purposes. In such cases, the study center staff will be kept blinded and the patient will not need to be disqualified from the study.

3.6 Monitoring Treatment Compliance

Study drug adherence will be emphasized at every visit. Study drug compliance during the DBTP will be closely monitored. The study staff will count the number of capsules remaining and compliance will be assessed based on the number of capsules prescribed and the number of capsules taken. Every effort will be made to collect unused study drug that has been dispensed to the patient. Any irregularities in study drug adherence should be discussed with the patient at every visit. Non-compliance is defined as taking less than 80% or more than 120% of study drug during any visit to visit evaluation period. Discontinuation for non-compliance will be at the Investigator's discretion and will to be recorded on the subject CRF. All errors in study drug dispensing or administration will be carefully documented in the subject study binder.

3.7 Prior and Concomitant Medications and Therapies

All medications taken and therapies received within 6 months prior to Screening must be noted on the eCRF. Medications taken and therapies received related to the primary indication (MDD) within the 5 years prior to Screening will also be recorded on the Concomitant medication CRF. The reported concomitant medications and/or therapies will be reviewed and evaluated by the Investigator to determine if they affect a subject's eligibility or continued participation in the study.

Medications for the acute treatment of extrapyramidal symptoms and akathisia are allowed, but should not be administered within 8 hours prior to movement disorder assessments. Zolpidem may be taken for insomnia, in the evening at bedtime and prior to midnight, but no more than 3 times per week during the Screening Period and the first 2 weeks of the DBTP only for the treatment of insomnia. Lorazepam (or other benzodiazepines) may be taken for anxiety, agitation, irritability, hostility, and restlessness. Daily doses should not exceed 3.0 mg/day during the Screening Period and through the first week of the DBTP. From Week 2 to week 6 daily dose should not exceed 2 mg/day. Doses may not be given on a standing basis, and the lowest effective dose should be used. Zolpidem or lorazepam, or their equivalents, should not administered within 8 hours prior to efficacy assessments. Any medication or therapy that is taken by or administered to the subject during the course of the study must be recorded in the ConMed CRF. The entry must include the dose, regimen, route, indication, and dates of use. All medications and other treatments taken by the subject during the study, including those treatments initiated before the start of the study, must be recorded on the ConMed CRF.

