Approach-Avoidance Learning Task. Participants are instructed to learn, through trial-and-error, which of three responses, indicated with distinct stimuli, to select to achieve a particular outcome. Critically, each response option is associated with a probability of *both* a reward outcome (points) *and* an aversive outcome (i.e., a mild electric shock). Consistent with reinforcement tasks, the response-outcome contingencies (e.g., which option is most likely to lead to reward) switch throughout the task, such that half the time the option that is most likely to lead to reward is also most likely to lead to a shock, and half the time the highest reward option is least likely to lead to shock. Thus, the task systematically manipulates congruency and conflict between reward-threat outcomes and additionally introduces a reversal learning^{61,147} probe for both reward and threat. To motivate adherence to instructions, participants are told they will receive monetary compensation in proportion to how well they perform. In contrast to fear conditioning tasks that instruct participants to select a shock intensity that nears painful (7/10 Likert scale), we would have participants select a level that is annoying and mildly uncomfortable (5/10) to enable tolerance of repeated stimulations, as the number of shocks delivered could be higher than during standard conditioning tasks. There would be 150 trials of the task. Each initial cue is presented until the participant makes a selection, followed by a jittered anticipation phase (2-4s), and then the threat outcome (mild electric shock) and reward outcome (points) would be presented sequentially and separated by a jittered ITI of 3-6s. Given that outcomes are driven probabilistically following participant choices, the total number of shocks delivered can vary.

8. Data Analysis

Describe the data analysis plan, including any statistical procedures or power analysis.

11. Statistical Analysis

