11.2 Statistical And Analytic Plan

The primary efficacy endpoint is the change from baseline to end of Week 6(EOT) in MADRS total score. Based on the primary hypothetical estimand strategy which assumes patients are on study drug up to the primary time point (end of Week 6), MADRS assessments collected off-treatment (ie, efficacy assessment performed more than 3 days after last dose of study drug) and/or after starting new treatment for MDD will be set to missing (except those collected for patients discontinued due to and will not be included in the primary analysis). The missing data in patients who discontinued due to lack of efficacy (LOE) or due to taking non-study treatment for MDD will be assumed missing-not-at-random. The missing data in patients who discontinued due to other reasons will be assumed as missing- at-random. Missing data will be imputed accordingly to recent recommendations using the ‘mice’ package in R.^{25,26}

The primary analysis will use a mixed-effects model for repeated measures (MMRM) to analyze the change from baseline to end of Week 6 in MADRS total score. Similar MMRM models will be used for secondary endpoints. An additional analysis will examine slopes of MADRS scores over the 6 week period, testing the hypothesis that the active drug group will have a steeper slope of MADRS over the 6 week period. Additional models will test for non-linear patterns of change as well. Similar analyses will be conducted on secondary outcomes (e.g. CGI, PTSD

symptom severity, etc.).

For imaging data, following standard preprocessing, beta coefficients of voxelwise brain activity will be defined using standard general linear models. These coefficients will be used in multivariate pattern analysis (MVPA) to build classifiers, using support vector machines (SVM), of reward and threat using leave-one-out cross-validation and quantify reward and threat anticipation during the task. MVPA classifier output will be analyzed using mixed effects models. Threat and reward anticipation as predictors of treatment outcome will be analyzed by including these variables as a predictor in the MMRM described above. Threat and reward anticipation as targets of treatment will be analyzed in mixed effects model with post-treatment classifier output as the dependent measure and including predictors of drug group and including pre-treatment classifier output as a covariate.

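### The 8-hour separation from lorazepam and zolpidem does not name the fMRI, so an Aim 2 scan shortly after as-needed lorazepam breaches nothing and its timing would not be recorded

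*Protocol*

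**What the plan says.** Section 3.7 of the protocol contains two 8-hour rules. Medication for extrapyramidal symptoms or akathisia "should not be administered within 8 hours prior to movement disorder assessments". For the sedatives, "Zolpidem or lorazepam, or their equivalents, should not administered within 8 hours prior to efficacy assessments". Neither rule mentions imaging.

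The permitted use in the same section changes over time:

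- Zolpidem is allowed "no more than 3 times per week during the Screening Period and the first 2 weeks of the DBTP only", taken "in the evening at bedtime and prior to midnight".
- For lorazepam or other benzodiazepines, taken for anxiety among other reasons and not on a standing basis, "Daily doses should not exceed 3.0 mg/day during the Screening Period and through the first week of the DBTP". Then: "From Week 2 to week 6 daily dose should not exceed 2 mg/day".

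Section 7.4 (Efficacy Assessments) describes the MADRS, the CGI-S and the EMA. The fMRI is described separately in Section 10. In Section 11.2 the scan data serve two purposes: as predictors added to the MMRM, and as treatment targets in a mixed model "with post-treatment classifier output as the dependent measure", with drug group as predictor and the pre-treatment output as covariate.

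**The concern.** By setting an interval for two kinds of measurement, the protocol accepts that recent medication can distort what is measured. It sets none for the measurement behind Aim 2. That measurement is anticipation of shock and reward, and lorazepam is permitted for anxiety. The risk section (item 39) acknowledges that some people become anxious on entering the magnet, and the task delivers mild electric shocks.

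If some scans are taken shortly after a benzodiazepine, three things are at stake: extra variability in the classifier output; a baseline value, used both as predictor and as covariate, that partly reflects recent sedation; and, if as-needed use after randomisation differs between arms, an arm difference at the second scan that is partly due to the sedative. A later analysis plan could not repair this. The concomitant medication record asks for dose, regimen, route, indication and dates of use, but not clock time, so a breach of an interval in hours could not be reconstructed for an as-needed drug.

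**Working it through.** There is no stated figure to reproduce. The check sets the passages side by side.

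**Step 1. Does any text attach a sedative interval to the fMRI?** The scans appear in form item 6 (Design and Methodology), item 7 (Study Procedure Description), Table 1, Section 4.2.2, Section 7.2.4 and Section 10. None attaches one.

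**Step 2. What is allowed at each scan date?**

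| | Pre-dose scan (Screening or Baseline) | Post-dose scan (Visit 8, Week 7) |
|---|---|---|
| Zolpidem | up to 3 times per week | outside its permitted period |
| Lorazepam ceiling | 3.0 mg/day | none stated; the last stated is 2 mg/day, ending at Week 6 |
| 8-hour rule naming the fMRI | none | none |

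The last stated ceiling is (3.0 − 2.0)/3.0 = 33% below the first. This compares ceilings; it does not measure use. Section 3.7.1 does not settle Week 7, because it refers for the permitted drugs to a Section 6.7 that this document does not contain.

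**Step 3. Which drug can fall inside 8 hours?** Zolpidem must be taken before midnight, and midnight + 8 h = 08:00, so it matters only for a scan starting before 08:00. Lorazepam and other benzodiazepines have no time-of-day limit and are the practical exposure.

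**Step 4. Does the MADRS bring the scan under the rule?** Table 1 schedules the MADRS at Visits 2 and 8, the two fMRI visits, so a scan directly after the MADRS would normally be covered. Three gaps remain:

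- Item 6 puts the pre-dose fMRI in the two-week Screening Period, while item 7 and Section 4.2.2 put it at Baseline. A scan on another Screening day has no MADRS attached to it.
- Section 7.2.4 lists the Visit 8 procedures with the fMRI but without any rating scale, unlike Table 1.
- Section 7.4 puts the MADRS first among the scales and does not place the fMRI in its recommended order. A dose taken after the MADRS and before the scan breaches nothing.

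**Step 5. Which analyses are exposed?** The ceilings bind both arms equally, so their change between dates does not by itself bias the comparison of arms on post-treatment output adjusted for pre-treatment output. Differential use after randomisation can. With 25 patients per arm, each patient scanned shortly after a sedative is 1/25 = 4 percentage points of an arm. The documents give no rate of use and no effect of sedation on the classifier output, so the calculation stops there.

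**The case against.** The strongest reply is that the gap is largely closed in practice. The MADRS falls on both scan visits and comes first among the scales, so the rule already governs dosing before those visits. Section 7.4 also refers to Table 1 for the efficacy assessments, and Table 1 has an fMRI row, so the term might be read to include the scan. A urine drug screen that includes benzodiazepines is repeated at Baseline. Medication use is recorded throughout, and imaging covariates and sensitivity analyses commonly belong in an analysis plan that is not shown. Imaging lies outside the confirmatory testing of Section 11.4.

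Much of this stands. The cover is real but partial, for the reasons in Step 4. The reading of Table 1 shows that the wording is ambiguous, which is itself a reason to settle it. The Baseline screen helps at the first scan if that scan is at Baseline, but the exclusion for a positive test (criterion 12) is tied to Visit 1, and Section 8 itself gives different occasions for drug testing. That exclusion also needs reconciling with the benzodiazepine allowance during Screening. The absence of a sensitivity analysis is no finding; the absence of clock time is, because it must be collected prospectively.

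A reader might infer more: that scans under sedation are likely, that placebo patients will use more lorazepam, or that the falling ceiling biases the drug effect. The documents support none of these. They give no usage data, item 39 says that people anxious on entering the magnet may be unable to take part, the shock level is self-selected to be non-painful, and the ceilings are the same in both arms.

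**Conclusion.** The point holds in a limited form. As written, the protocol permits an Aim 2 scan shortly after as-needed lorazepam or another benzodiazepine, and its records would not show how shortly. The consequences are possible noise and a possibly contaminated baseline predictor or covariate. Bias in the second-scan arm contrast arises only on the assumption that as-needed use differs by arm. The size cannot be estimated from the documents. The MADRS primary analysis and the key secondary analyses are not affected. The Week 7 allowance is a separate gap in the text to be reconciled. This is a cheap improvement to the imaging part of the trial, not a flaw in its main comparison.

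**What to change.** 1. Reconcile Sections 3.7 and 10 so that the existing 8-hour separation is expressly stated to apply, or not to apply, to both fMRI sessions. Reconcile the timing of the first scan (Screening or Baseline) and the Visit 8 procedure list with Table 1.
2. Schedule each scan to respect the interval the protocol already uses for its other measurements, moving the scan within the visit window where needed.
3. Record the clock time and dose of the last benzodiazepine or hypnotic before each scan, and summarise this by arm and scan.
4. Keep all scans in the main imaging model. Any analysis without scans inside the interval should be supportive only: exclusion at the second scan conditions on behaviour after randomisation and can itself introduce selection bias.
5. The sponsor should reconcile the lorazepam wording, which ends at Week 6, with the Week 7 scan, and correct the reference in Section 3.7.1 to a Section 6.7 that does not exist. No dose or clinical rule is proposed here.

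The cost is a clarified passage in the protocol, one CRF field and an occasional rescheduled scan.
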